	
 B. External Ocular Examination C. Schirmer-I test without anesthesia D. Slit Lamp Examination (SLE) of the anterior segment of the eye (cornea, conjunctiva, anterior chamber, iris, lids and lashes) E. Assess bulbar redness (VBR 10) F. Instill fluorescein and wait 30 seconds. G. Assess FTBUT. H. After 2-5 minutes from the time of fluorescein instillation, assess total corneal fluorescein staining score (NEI scale score range 0-15). I. Instill lissamine green. J. Assess total conjunctival lissamine green staining score (NEI scale, score range 0-18) within 2 minutes of instillation of dye. 
 
 6. Inclusion/exclusion criteria assessment by the investigator 7. Dispense the Study Product (vehicle) eye drops to be instilled; the first eye drop will be instilled by the Investigator in both eyes and then the Study Product (vehicle) will be instilled by the patient at home 3 times a day in both eyes for 12 days ± 2. Depending on the time of the Subject's baseline visit, all doses may not be administered on this day. 8. Deliver instructions to patient. 9. Dispense the Patient Diary to record the administration of Study Product (vehicle) during the Run-In period (vehicle accountability), any new or changes in concomitant medications, any unusual medical condition. 10. Investigator documentation of the first administration of the Study Product (vehicle) in the patient's medical record following Visit 1 to confirm the first administration of the Study Product (vehicle). 11. AE monitoring 
 
 RUN-IN period (from Day -12 to Day 1): At home, patients will proceed with the Run-In of 12 days ± 2 using the dispensed Study Product (Vehicle) eye drops (1 drop in both eyes, 3 times a day). No other ophthalmic topical medications are permitted. 
 
 Visit 2 (Day 1): BASELINE Patients will be randomized if they continue to meet eligibility criteria at Visit 2/Baseline. 
 
 1. Concomitant Ocular and Systemic Medications and Conditions 2. Record AEs 3. Pregnancy test 4. SANDE questionnaire 5. CCI 

Information	Description

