8.3 ASSESSMENTS AND CLINICAL DEFINITIONS

Table 6: List of assessments

Assessment type	Parameters to be analyzed (units)
SANDE questionnaire	
SANDE questionnaire includes two CCI-based questions that assess:
 
 (i) DED symptom frequency (from 0 to 100) (ii) DED symptom severity (from 0 to 100) 
compiled by the patients.
 
The global SANDE score (from 0 to 100) is calculated by multiplying the frequency score by the severity score and obtaining the square root.
 
SANDE is copyrighted by Massachusetts Eye and Ear Infirmary (MEEI). A license will be purchased prior to use in the clinical trial.

CCI	
Scores for sub-scales within the dimensions of CCI (intensity 24h and past 2 weeks: 0-10), CCI (intensity: 0-10, time spent thinking about CCI 0-100%), CCI (interference in activities of daily life: 0-10, time spent thinking about CCI CCI
 
CCI CCI CCI is a validated questionnaire that is copyrighted by the CCI CCI A license will be purchased prior to use in the clinical trial. This form will be administered to all subjects but completed only by those that either have CCI or have filled this form before.

NIKBUT	
Non-Invasive Keratograph tear Break-Up Time (measured in seconds) will be assessed at select centers that have the Oculus keratograph 5M (Oculus, Inc., Arlington, WA) Two types of NIKBUT will be collected:
 
 (i) NIKBUT-first is the time at which the first distortion is recorded, (ii) NIKBUT-average is the average time of first breakup incidents in different cornea locations during recording
Schirmer-I without anesthesia	
After NIKBUT, but prior to slit-lamp examination and vital dye staining, Schirmer-I test will be performed without anesthesia to determine wetting of the strip within 5 minutes and the length of the moistened strip will be measured in millimeters (mm).

Slit lamp examination	
A slit-lamp examination of ocular adnexa (lids, lashes, conjunctival fornix, lacrimal gland and drainage) and anterior segment (cornea, conjunctiva, aqueous humor, iris, lens, vitreous humor) will be performed using white light and prior to vital dye instillation.

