4.5.2. Key Secondary and Secondary Endpoints

For the efficacy inferential analysis, missing data on key secondary and secondary endpoints will be imputed using the imputation methods described in [Section 8.2.1.2](#) or [Section 8.2.1.3](#), depending on the nature of the data. Descriptive analyses will be based on observed data.

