Mean change from baseline in total CCI [REDACTED] in the Study Eye as assessed by the investigator at week 8

Actual values and changes from baseline to Week 8 in total CCI [REDACTED] will be summarized by means of descriptive statistics for the Study Eye.

The ANCOVA model and the imputation strategy described in [Section 8.2.1.2](#) will be applied to the change from baseline of total CCI scale in Study Eye at Week 8.

Mean change from baseline in symptoms questionnaire (SANDE) scores for severity and frequency at weeks 4 and 8

Actual observed values and changes from baseline to Week 4 and Week 8 in SANDE scores for severity and frequency will be summarized by means of descriptive statistics.

The ANCOVA model described in [Section 8.2.1.2](#) and the imputation strategy described in [Section 8.1.1](#) will be applied to SANDE symptoms questionnaire severity scores and frequency scores in Study Eye at Week 4 and Week 8 separately.

Mean change from baseline in symptoms of dry eye assessed by SANDE Global Score at week 4

Actual observed values and changes from baseline to Week 4 in SANDE Global Score will be summarized by means of descriptive statistics.

Comparisons between each active treatment and vehicle will be performed within the MMRM model described for the primary endpoint (see [Section 8.1](#)) to maintain the results consistent. For this reason, the same strategy used for the ICEs established for the primary endpoint will also be applied to this endpoint regardless of being secondary only.

Mean change from baseline of the CCI at weeks 4 and 8

CCI The score for each subscale is defined as sum of scores divided by number of questions answered within each subscale. The percentage values will be divided by 10 before applying the algorithm. Symptom relief is not assessed at Baseline.

CCI will be calculated as the sum of the scores for CCI intensity at 24 hours and 2 weeks (questions 4-9) divided by the number of questions answered for questions 4-9. CCI has a score range of 0-10.

Actual values and changes from baseline to Week 4 and Week 8 in Ocular Pain Score (assessed by OPAS questionnaire) will be summarized by means of descriptive statistics.

The ANCOVA model and the imputation strategy described in [Section 8.2.1.2](#) will be applied to the CCI at Weeks 4 and 8 separately.

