13.1. Schedule of Activities

	Run-In period		Treatment period		Follow-up period
	V1 Screening (Day -12)	V2 Baseline (Day 1)	V3 Week 2 (Day 13)	V4 Week 4 (EOT) (Days 28)*	V5 Week 8 (EOS) (Days 56)*
Interval Tolerance (days)	±2		±1	±1	±2
Site Visit	X	X	X	X	X
ELIGIBILITY					
Informed consent	X				
Inclusion / Exclusion criteria	X	X			
Demographics, Medical History, Medications	X				
TRIAL INTERVENTIONS					
Randomization		X			
Trial Study Product dispensation**	X	X	X		
Artificial tears dispensation				X	
Patient Instruction	X	X		X	
Application of CCI by the investigator	X				
Patient's Diary dispensation	X	X		X	
Documentation in patient's medical record of first dose administration by Investigator	X				
Medication dosing compliance verification (diaries)		X	X	X	X

TRIAL PROCEDURES					
Check the Patient Diary		X	X	X	X
SANDE questionnaire	X	X		X	X
CCI [REDACTED]	CCI [REDACTED]				
BCDVA by ETDRS	X	X		X	X
External Ocular Examination	X	X		X	X
CCI [REDACTED]	CCI [REDACTED]				
Schirmer-I test without anesthesia	X	X		X	X
Slit Lamp Examination	X	X		X	X
Redness score (VBR 10)	X	X		X	X
Instill fluorescein	X	X		X	X
fTBUT	X	X		X	X
CCI [REDACTED]	CCI [REDACTED]				
CCI [REDACTED]	CCI [REDACTED]				
Conjunctival lissamine green Staining NEI scale.	X	X		X	X
CCI [REDACTED] before and after CCI [REDACTED] ***	CCI [REDACTED]				
Specular microscopy (Corneal endothelial cell density) (in selected centers)		X			X
Instill tropicamide CCI [REDACTED]		X			X
Dilated fundus examination		X			X
Collect used/unused Study Product (to be checked by independent personnel)		X	X	X	

Retrieve Patient Diary		X		X	X
Concomitant medications****		X	X	X	X
Adverse events evaluation		X	X	X	X
LABORATORY TESTS					
Pregnancy Test	X	X		X	

*In case of premature discontinuation of the study, the patient will be required to participate at the Early Exit Visit that will have the same assessment of Visit 4 (in case of early treatment discontinuation before Visit 4) or the same assessment of Visit 5 (in case the discontinuation from the study will occur after the ending of the treatment but before the expected Visit 5). A flag will be inserted in the eCRF to define if the Visit 4 or 5 is a per protocol visit or if it is done as Early Exit Visit.

** An CCI kit will be also provided

^ CCI will be administered to all subjects but completed only by those that either have CCI or have filled this form before.

*** Only in patients with CCI >0

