13.3. SAS Code for Primary Analysis

Step 1: Multiple Imputation

```
PROC SORT data=efficacy;  
  by USUBJID;  
RUN;
```

```
PROC MI data=efficacy nimpute=50 out=mi_data min=0 max=100 seed= 47292748; *score range: 0-100;  
  class TRTPN;  
  var V2 V4 V5; *V2=baseline, V4=Week 4, V5=Week 8;  
  FCS regression;  
  mnar model(V2 V4 V5/ modelobs=(TRTPN='3')); *Vehicle group has TRTPN=3;  
RUN;
```

Data will be transformed to short format by AVISITN before applying multiple imputation.
The MI method will be used for both primary and secondary analyses after applying appropriate ICE handling strategies.

Step 2: MMRM Model

```
PROC MIXED data= mi_data_long;  
  by _imputation;  
  class TRTPN AVISITN USUBJID;  
  model CHG=BASE TRTPN AVISITN TRTPN*AVISITN / DDFM=KR CL;  
  repeated AVISITN/subject=USUBJID type=UN;  
  lsmeans TRTPN*AVISITN/diff cl;  
  ods output lsmeans=lsM diffs=diffM;  
RUN;
```

Data will be transformed back to long format by combining visits before applying MMRM model.
If model fails to converge, the “type=UN” will be replaced by “type=CS”.
This model is the essential model for primary endpoint. Appropriate adjustments may be made based on modified Estimand strategies and sensitivity analyses.

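### Patients without ocular pain at baseline have no OPAS baseline, and the planned imputation fills it from patients with pain, so new on-treatment pain is understated or lost

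*Protocol*

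**What the plan says.** - **Who completes the form.** Protocol 8.3, Table 6: "This form will be administered to all subjects but completed only by those that either have CCI or have filled this form before". SAP 13.1 repeats the rule in a footnote: "completed only by those that either have CCI or have filled this form before". CCI marks redacted text.
- **When.** Protocol Table 1 schedules the form at Visits 2, 4 and 5. The synopsis list for Visit 2 shows it directly after SANDE ("3. Pregnancy test 4. SANDE questionnaire 5. CCI"); the Visit 1 list has no such item.
- **What it is.** SAP 8.2.2.1 names it once without redaction: "in Ocular Pain Score (assessed by OPAS questionnaire) will be summarized by means of descriptive statistics".
- **Scoring.** The pain score is the sum of items 4-9 "divided by the number of questions answered for questions 4-9", with range 0-10. The QoL score averages items 13-19 in the same way. No visible rule gives a score to a form left blank.
- **Baseline.** SAP 4.4.1 replaces a missing baseline by the last value before first dose, if there is one.
- **Missing data.** SAP 4.5.2, for inferential analysis: "missing data on key secondary and secondary endpoints will be imputed using the imputation methods described in" SAP 8.2.1.2 or 8.2.1.3. SAP 8.2.2.1 gives the pain and QoL scores the ANCOVA and imputation of 8.2.1.2, which refers to 8.2.1.1 and through it to 8.1.1. There, baseline and later values are imputed from a model fitted to vehicle observations only. The code in SAP 13.3 has Visit 2 in that model, and its note reads: "The MI method will be used for both primary and secondary analyses after applying appropriate ICE handling strategies".

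**The concern.** The completion rule works in one direction only. A patient with pain at Visit 2 goes on completing the form, so resolution is measured. A patient whose pain starts on treatment completes it for the first time at Visit 4 or 5, so onset has no starting value. The blank at Visit 2 is not a lost measurement. It reflects the absence of the condition, yet the visible rules treat it as missing and fill it from patients who have the condition.

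This matters because the new concentrations were chosen largely for tolerability. Protocol 6.2 cites eye pain in 42% to 63.5% of patients in earlier dry eye studies. If new pain is more frequent on rhNGF, an analysis that understates it moves the between-arm pain difference toward no harm. Protocol 10.6.2 also lets secondary results inform the choice between concentrations if both succeed.

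**Working it through.** The documents give no OPAS mean, SD, correlation or pain-free share, so there is no plan figure to reproduce. The first step is textual; the others rest on stated assumptions.

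**1. The route to a painful baseline**
- Nobody can have filled the form before Visit 2, so at that visit only patients with the condition complete it.
- For the others, the SAP 4.4.1 fallback finds no earlier value.
- Protocol 10.6.4 says the key secondary imputation uses baseline and week 4 data, so baseline is part of that procedure.
- The imputation model uses vehicle observations only, and every observed vehicle value at Visit 2 comes from a patient with the condition.
- Forms left blank at later attended visits are filled in the same way.

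**2. Expected analysed change for one new-pain patient**

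Assumptions: vehicle completers have mean m2 at baseline and m4 at week 4, equal SDs and correlation r. For a patient with blank baseline and week 4 score y:
- expected imputed baseline = m2 + r(y − m4)
- expected change = y − m2 − r(y − m4)
- break-even score, where this is zero: y* = (m2 − r·m4)/(1 − r)

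Central case, m2 = 5, m4 = 4, r = 0.5: y* = (5 − 2)/0.5 = 6.0. Over m2 from 4 to 6, a vehicle change of 0 or −1, and r from 0.3 to 0.7:
- lowest (m2 = m4 = 4, any r): y* = 4.0
- highest (m2 = 6, m4 = 5, r = 0.7): y* = (6 − 3.5)/0.3 = 8.3

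**3. Simulation of the planned procedure**

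Settings: 97 per arm; vehicle-only regression imputation of baseline and week 4, limited to 0-10, then ANCOVA; 80 runs per setting. Assumptions: m2 of 4, 5 or 6; SD 2; r = 0.5; vehicle change −1; 30% or 60% pain-free at baseline; new pain in 10% of these on vehicle and 48% on active. The 48% borrows one of the eye-pain rates in Protocol 6.2 as an upper-end value. The comparison scores a pain-free baseline as 0.

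| New week 4 score (about) | Change if baseline is 0 | Expected analysed change, central case | Simulated mean analysed change, new-pain active patients | Share shown as improved |
|---|---|---|---|---|
| 2 | +2 | −2.0 | −1.4 to −2.5 | 78-91% |
| 4 | +4 | −1.0 | −0.4 to −1.5 | 58-79% |
| 6 | +6 | 0.0 | −0.5 to +0.6 | 39-61% |
| 8 | +8 | +1.0 | +0.5 to +1.6 | 22-40% |

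Over all settings the ANCOVA difference (active minus vehicle, positive = worse on active) is +0.2 to +1.9 with pain-free baselines scored 0, and −0.6 to +0.9 under the planned imputation. It shrinks in every setting and changes sign in all settings with new pain of about 2.

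**4. Dependence on the pain-free share**

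If only new pain separates the arms, the true difference is roughly share × (0.48 − 0.10) × new score. For a new score of 4:
- 5% pain-free: 0.05 × 0.38 × 4 = 0.08
- 10%: 0.15
- 30%: 0.46
- 60%: 0.91

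**5. If baseline is not imputed**

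A patient with no baseline has neither a change score nor a covariate and leaves the ANCOVA. The new pain is then lost from the comparison but not reversed.

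**The case against.** - **Redaction.** The gating word is blacked out, as is text close to the scoring sentence and the secondary-endpoint rule in SAP 8.2.2, where a rule for blanks could sit. This stands: that blanks are true zeros is an inference. It is a strong one, since the form is OPAS and Protocol 6.2 prints eye pain where the amendment summary redacts the same sentence. If the condition were something else, scoring 0 would be wrong, though the missing baseline would remain.
- **Observed data.** SAP 8.2.2 says observed values are used for secondary endpoints. That clause concerns intercurrent events. The same section separately marks the domain summaries as needing no imputation, which implies that the main scores are imputed.
- **Week 4 only.** SAP 8.2.1.2 speaks of imputing missing Schirmer scores at week 4, and the baseline step in 8.1.1 is written for SANDE. Non-imputation of baseline is therefore a possible reading; it loses the patients rather than reversing them.
- **New pain is seen elsewhere.** Ocular TEAEs are tabulated by eye (SAP 9.1) and discontinuations for tolerability are counted (SAP 9.3). Protocol 9.2 requires clinically relevant worsening on a questionnaire to be reported as an AE. Observed OPAS scores are summarised at each visit, and the domains are also compared on observed values. This stands, so a reader who infers that the plan conceals drug-induced pain goes too far.
- **Inputs.** The cited 42% to 63.5% are patients reporting eye pain in earlier studies. They are not rates of new pain in pain-free patients at a visit. Entry requires SANDE of at least 50, so the pain-free share may be small. This stands for the size, not for the mechanism.

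**Conclusion.** The flaw is real and limited. As visibly written, patients without the condition at Visit 2 either receive a baseline drawn from patients with it or leave the ANCOVA. In both cases new on-treatment pain is not counted as measured. If it is more frequent on rhNGF, the between-arm difference is pulled toward no harm.

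A reader might infer that the imputation regularly turns worsening into improvement, or that it creates an apparent pain benefit for rhNGF. The documents support neither as a general statement. The sign of a patient's change is expected to reverse only below a break-even of about 4 to 8 (6 in the central case), which rests on assumed OPAS values; more severe new pain still shows as a smaller worsening. With new pain of about 4, the simulated planned difference lies near zero (−0.2 to +0.2) rather than clearly favouring rhNGF. Imputing pain scores for patients who never have pain would also dilute a true pain benefit.

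The affected results are the OPAS pain and QoL scores. SAP 8.2.2.1 calls the secondary results descriptive and leaves them outside alpha control. The primary and key secondary analyses are untouched. The correction is worth making because it is cheap and the endpoint bears on tolerability.

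**What to change.** Unless redacted text already does so, add to SAP 8.2.2.1:
- **Pain intensity.** At an attended visit where the form was skipped because ocular pain was absent, set the score to 0 before imputation. Apply multiple imputation only to assessments that were truly missed.
- **QoL.** Do not impute structurally blank scores from patients with pain. Analyse QoL in patients with an observed baseline. At most, score blanks 0 in a sensitivity analysis, because absence of pain does not establish absence of interference with daily life.

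For patients still to be assessed, remove the skip rule from Protocol Table 1 and Table 6 so that everyone completes the form at Visits 2, 4 and 5.

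Cost: a short SAP addition and a programming rule that works on data already collected, provided that a blank due to absent pain can be told from a form missed for another reason; no visible text says that this reason is recorded. Completion by all patients adds a few minutes at visits already held.

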8.4 PHARMACOKINETICS

No samples for pharmacokinetic evaluations will be collected during the study.

8.5 GENETICS

No sample for genetic analyses will be collected during the study.

8.6 BIOMARKERS

No sample for Biomarker assessment will be collected during the study.

8.7 IMMUNOGENICITY ASSESSMENT

No sample for immunogenicity assessment will be collected during the study.

9 EVALUATION OF ADVERSE EVENTS AND SAFETY INFORMATION

9.1 DEFINITIONS

9.1.1 Adverse Event

An **Adverse Event (AE)** is defined as any untoward medical occurrence in a patient or clinical investigation subject administered a medicinal product and which does not necessarily have a causal relationship with this treatment. An AE can therefore be any unfavorable and unintended sign (including an abnormal laboratory finding), symptom, or disease temporally associated with the use of a medicinal product, whether or not related to the medicinal product.

9.1.2 Adverse Drug Reaction

An **Adverse Drug Reaction (ADR)** is defined as any noxious and unintended response to a medicinal product related to any dose. Any responses to a medicinal product means that a causal relationship between a medicinal product and an adverse event is at least a reasonable possibility, i.e., the relationship cannot be ruled out.

The definition also covers medication errors and uses outside what is foreseen in the protocol, including misuse and abuse of the product. For the purposes of regulatory safety reporting, “reasonable possibility” means there are facts (evidence) or arguments to suggest a causal relationship between the drug and the adverse event. Adverse events are to be considered unrelated if the relationship to the study drug, as described in the table in § 9.3.2, is none or unlikely; whereas any AE reported in the study having a possible, probable or highly probable relationship to study drug will be considered as an ADR.

9.1.3 Serious Adverse Event

A **Serious Adverse Event (SAE)** is defined as any adverse experience that, in the view of either the Investigator or Sponsor, meets any of the following criteria:

- results in death,
- is life-threatening (i.e., the patient was at immediate risk of death at the time of the event. It does not refer to an event which hypothetically might have caused death if it were more severe),
- requires inpatient hospitalization or prolongation of existing hospitalization.

NOTE: In general, hospitalization means that the individual remained at the hospital or emergency ward for observation and/or treatment (usually involving an overnight stay) that would not have been appropriate in the physician's office or an outpatient setting. Complications that occur during hospitalization are AEs. If a complication prolongs hospitalization or fulfills any other serious criteria, the event is serious. When in doubt as to whether “hospitalization” occurred, the event should be considered serious.

- results in persistent or significant disability/incapacity.

NOTE: The term disability means a substantial disruption of a person's ability to conduct normal life functions. This definition is not intended to include experiences of relatively minor medical significance such as uncomplicated headache, nausea, vomiting, diarrhea, influenza, or accidental trauma (e.g., sprained ankle) which may interfere or prevent everyday life functions, but do not constitute a substantial disruption.

- is a congenital anomaly/birth defect,
- is an important medical event.

NOTE: An important medical event is an event that may not result in death, be life threatening, or require hospitalization, but may be considered a SAE when, based upon appropriate medical judgment, it may jeopardize the patient's wellbeing and may require medical or surgical intervention to prevent one of the outcomes listed in the definitions for SAEs. Examples of such medical events include allergic bronchospasm requiring intensive treatment in an emergency room or at home, blood dyscrasias or convulsions that do not result in patient hospitalization or the development of drug dependency or drug abuse.

Pre-planned hospitalization or hospitalization for routine treatment or monitoring of the studied indication, not associated with any deterioration in condition are not considered to be SAEs (see § 9.4.2). These events must be recorded in the AE page of the eCRF where a variable will be ticked to indicate that they are not SAEs.

Death shall always be reported as SAE and cause of death shall always be specified when known.

